6.3.1 DOSE DELAY/MODIFICATIONS: UMBRALISIB

Supportive care should be considered for any subject who experiences Grade \geq 2 cytopenias, or Grade \geq 1 non-hematologic toxicities. Delay for recovery from toxicity is allowed for both study drugs (ublituximab and/or umbralisib) for recovery of hematologic toxicities to \leq Grade 3 or non-hematologic toxicities to \leq Grade 2 or to baseline level. If the subject withdraws consent or has documented progression, an end of study visit should be completed.

If a subject discontinues only one study drug, the subject may continue treatment with the other study drug per the protocol.

TABLE 2: UMBRALISIB DOSE DELAY AND/OR MODIFICATIONS GUIDANCE

NCI-CTCAE Grade	Dose Delay and/or Modification
Hematologic Adverse Event	
Neutropenia	
Grade \leq 2 neutropenia	Maintain current dose. Consider supportive care as warranted.
Grade 3 neutropenia	Maintain current dose, consider supportive care. If recurrence or persistent Grade 3, resume at next lower dose level at discretion of the investigator.
Grade 4 neutropenia or occurrence of neutropenic fever or infection	Delay umbralisib until Grade \leq 3 and/or neutropenic fever or infection is resolved; thereafter, resume at full dose. Consider supportive care. If recurrence after re-challenge, resume at next lower dose level at discretion of the investigator.
Thrombocytopenia	
Grade \leq 3 thrombocytopenia	Maintain current dose level and provide supportive care as clinically warranted.
Grade 4 thrombocytopenia	Delay umbralisib until Grade \leq 3; thereafter, resume at full dose. Consider supportive care intervention as warranted. If recurrence after re-challenge, resume at next lower dose level at discretion of the investigator.
Pulmonary & Related Infections*	
Grade 2	Stop all therapy and hold until resolution. Restart umbralisib at current dose or one lower dose level per PI discretion. Subjects with Grade 1 or 2 pneumonitis must restart at one lower dose level. If recurrence after re-challenge, resume at next lower dose level at discretion of the investigator.
Grade \geq 3	Stop all therapy and hold until resolution. Restart umbralisib at one lower dose level per PI discretion. Subjects with Grade \geq 3 pneumonitis must discontinue therapy.
All Other Non-Hematological Adverse Events	
Grade \leq 2	Maintain current dose level. NOTE: If persistent grade 2 diarrhea, despite supportive care, delay umbralisib until \leq grade 1. If recurrence after re-challenge, resume at full dose or next lower dose level at discretion of the investigator.
Grade \geq 3	Withhold umbralisib until Grade \leq 2. If recurrence after re-challenge, resume at full dose or next lower dose level at discretion of the investigator.
Diarrhea and/or Colitis	
Diarrhea Grade \leq 2	Maintain current dose level if tolerable or hold and then resume at current dose level once has resolved. NOTE: If persistent grade 2 diarrhea, despite supportive care, delay umbralisib until \leq grade 1. If recurrence after rechallenge, resume at full dose or next lower dose level at discretion of the investigator.

Diarrhea Grade ≥ 3	Withhold umbralisib until Grade ≤ 2 . Resume at full dose or next lower dose level as per discretion of investigator If recurrence after rechallenge, resume at next lower dose level at discretion of the investigator.
Colitis (all Grades)	Hold umbralisib. Treat with supportive care and after resolution of colitis, resume umbralisib at next lower dose level
Liver Toxicity (ALT/SGPT, AST/SGOT, Bilirubin, Alkaline Phosphatase)	
Grade 1	
 Maintain current dose Assess Concomitant Medications and Risk Factors* Monitor Labs every 1-2 weeks
Grade 2	
 Maintain current dose Assess Concomitant Medications and Risk Factors* Begin supportive care (prednisone 0.5-1 mg/kg/day or equivalent, per investigator discretion)** Monitor labs at least weekly until Grade 1 Once resolved to Grade ≤ 1, taper prednisone by 10 mg per week until off. If liver toxicity recurs to Grade 2 once off steroids, re-initiate steroids with 10 mg per week taper until off. 
 Consider withholding umbralisib.
Grade > 3	
 Hold umbralisib Assess Concomitant Medications and Risk Factors* Begin/continue supportive care (0.5-1 mg/kg/day or equivalent, per investigator discretion)** Monitor labs at least weekly until Grade 1 Once resolved to Grade ≤ 1, taper prednisone by 10 mg per week until off Resume umbralisib at next lower dose level when Grade ≤ 1

* Assess for disorders of lipids and glucose, thyroid disorders, alcohol use, viral infections, etc.

**Supportive Care – Aggressive management of lipid, glucose, other metabolic disorders, viral infections, etc. Important: Before initiating steroids, check for viral hepatitis or CMV infection.

STUDY DRUG DOSE REDUCTION RECOMMENDATIONS

Study Drug	Starting Dose	1 st Dose Reduction	2 nd Dose Reduction
Umbralisib	800 mg	600 mg	400 mg

A maximum of two dose level reductions are allowed for umbralisib.

If a subject requires a dose reduction of umbralisib due to study drug related toxicity, the dose may not be re-escalated. If further evaluation of the toxicity reveals the event was not related to umbralisib, this must be recorded in the medical record and dose re-escalation to the next higher dose level may be considered at the discretion of the investigator.

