6.3.2 DOSE DELAY/MODIFICATIONS: UBLITUXIMAB

No reduction in the dose of ublituximab is permitted. Please refer to Section 6.2.2.1 for detailed information on infusion rate guidance for infusion related reactions related to ublituximab.

Supportive care should be considered for any subject who experiences Grade ≥ 2 cytopenias, or Grade ≥ 1 non-hematologic toxicities. A delay for recovery from toxicity is allowed for both study drugs (individually or together) for recovery of hematologic toxicities to \leq Grade 3 or non-hematologic toxicities to \leq Grade 2 or to baseline level. If the subject withdraws consent or has documented progression, an end of study visit should be completed.

If Grade 4 anaphylaxis is observed at any point during ublituximab treatment, permanently discontinue ublituximab treatment and intervene as per investigator discretion.

If a subject discontinues only one study drug (either ublituximab or umbralisib), the subject may continue treatment with the other study drug per the protocol. **Contact the sponsor prior to discontinuing the study drug(s).**

TABLE 3: UBLITUXIMAB DOSE DELAY AND/OR MODIFICATIONS GUIDANCE

NCI-CTCAE Grade	Dose Delay and/or Modification
Hematologic Adverse Event	
Neutropenia	
Grade \leq 3 neutropenia	Maintain current dose. Consider supportive care as warranted.
Grade 4 neutropenia or occurrence of neutropenic fever or infection	Delay ublituximab until Grade \leq 3 and/or neutropenic fever or infection is resolved; consider growth-factor support as warranted; thereafter, resume at full dose.
Thrombocytopenia	
Grade \leq 3 thrombocytopenia	Maintain current dose and provide supportive care as clinically warranted.
Grade 4 thrombocytopenia	Delay ublituximab until Grade \leq 3; consider intervention with supportive care as warranted; thereafter resume at full dose.
Non-Hematological Adverse Events	
Grade \leq 2	Maintain current dose.
Grade \geq 3	Withhold ublituximab until Grade \leq 2 at the discretion of the investigator; consider supportive care intervention as warranted. Resume at full dose.

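### For a Grade 2 pulmonary event, Table 2 stops all therapy while Table 3 keeps ublituximab going, and the Grade ≥3 instructions for ublituximab do not match either

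*Combined protocol and SAP*

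**What the plan says.** Section 6.3 refers the reader to Sections 6.3.1 and 6.3.2 for dose delay and modification. It does not say which applies if they differ.

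Table 2 (Section 6.3.1, umbralisib) has its own block for pulmonary events and related infections:

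- Grade 2: "Stop all therapy and hold until resolution. Restart umbralisib at current dose or one lower dose level per PI discretion". The same row adds "Subjects with Grade 1 or 2 pneumonitis must restart at one lower dose level".
- Grade ≥3: "Stop all therapy and hold until resolution. Restart umbralisib at one lower dose level per PI discretion". The row then says that subjects with pneumonitis of this grade fall under "pneumonitis must discontinue therapy".

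The next block of Table 2 is headed "All Other Non-Hematological Adverse Events".

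Table 3 (Section 6.3.2, ublituximab) has no pulmonary or pneumonitis row. Its non-hematological block carries no exception. At Grade ≤2 the current dose is maintained. At Grade ≥3 ublituximab is withheld until Grade ≤2, "at the discretion of the investigator; consider supportive care intervention as warranted. Resume at full dose".

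Sections 6.3, 6.3.1 and 6.3.2 each allow a subject who stops one study drug to continue the other.

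**The concern.** A site facing a pulmonary event on an infusion day needs one answer for each drug. The two tables appear to give ublituximab different answers, and neither refers to the other. Two sites following the protocol faithfully could treat the same event differently. Pneumonitis is also one of the four toxicities that Section 4.2 uses to define an unacceptable run-in event, so its handling should be the clearest in the protocol. What is at stake is subject safety and consistent conduct across up to 15 centers.

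**Working it through.** No formula applies to the core of this point. The check sets the instructions for ublituximab side by side.

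| Event | Table 2 (6.3.1) | Table 3 (6.3.2) | Result |
|---|---|---|---|
| Grade 2 pneumonitis or related infection | Stop all therapy, hold until resolved | Maintain dose | Direct contradiction |
| Grade ≥3 pulmonary event other than pneumonitis | Stop all therapy, hold until resolved | Withhold at discretion until Grade ≤2, then full dose | Both interrupt; discretion and restart threshold differ |
| Grade ≥3 pneumonitis | Therapy must be discontinued, drug not named | Withhold at discretion until Grade ≤2, then full dose | Contradiction only if *therapy* includes ublituximab |
| Grade 1 pneumonitis | Restart rule one level lower, placed in the Grade 2 row; no hold stated | Maintain dose | Restart without a hold in Table 2 |

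**Step 1: does *all therapy* include ublituximab?** Table 2 is titled for umbralisib, so this has to be argued. Its other interruption rows (neutropenia, thrombocytopenia, diarrhea, colitis, liver) name umbralisib as the drug to delay, withhold or hold. Only the pulmonary rows say *all therapy*, and their next sentence goes back to naming umbralisib for the restart. The text above the table also covers both drugs: "Delay for recovery from toxicity is allowed for both study drugs (ublituximab and/or umbralisib"). The natural reading is that the stop applies to both drugs and the restart sentence to umbralisib. On that reading Table 2 gives no restart rule for ublituximab.

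**Step 2: does Table 3 reach pulmonary events?** Its non-hematological heading is unqualified and nothing is carved out, so it does.

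**Step 3: does any other text break the tie?** The introductory text of 6.3.1 and 6.3.2 allows delay until non-hematologic toxicity is Grade ≤2 or at baseline. A Grade 2 event already meets the first of these, so that text does not settle whether to stop. It also differs from holding until resolution. Sponsor contact is required before a drug is discontinued, not before a Grade 2 decision to hold or infuse.

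**Step 4: Grade 1 pneumonitis.** Table 2's general Grade ≤2 row, which maintains the dose, sits under the heading for all *other* non-hematological events. It therefore arguably does not cover pneumonitis. That leaves no Grade 1 instruction to hold, only one to restart.

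**Step 5: exposure window.** Planned ublituximab infusions (Section 6.1) are 3 in Cycle 1, 5 in Cycles 2 to 6, and 2 in Cycles 9 and 12: 3 + 5 + 2 = 10. After Cycle 12 no ublituximab is given, so the conflict on that drug can no longer arise.

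**The case against.** The strongest reply is that only Grade 2 is a true conflict. At Grade ≥3 both tables interrupt ublituximab for infections. For pneumonitis, the unnamed *therapy* stands in an umbralisib table, and three sections let the other drug continue. If *therapy* means umbralisib alone, nothing is contradicted. This stands: the Grade ≥3 rows are mismatched and ambiguous, and should not be called opposite.

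A second reply concerns completeness. The pulmonary heading carries an asterisk, and the only visible single-asterisk note concerns liver risk factors. The Summary of Changes for Version 2.0 describes a statement letting umbralisib continue, at investigator discretion, for sinopulmonary infections clearly unrelated to immune-mediated pneumonitis. A footnote to that effect may exist but is not visible in the text available for review. This also stands. The infection part is less certain than the pneumonitis part, and no error is inferred from the missing note.

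Third, both tables are headed as guidance, and Section 6.3 allows dosing only when clinical and laboratory findings are acceptable. These safeguards leave room for judgment, but they do not tell a site which table to follow at Grade 2.

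A reader might also infer that the conflict changes the 3+3 count. The documents do not support that:

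- Section 4.2 counts pneumonitis in Cycle 1 if it is Grade ≥3 and lasts more than 7 days, or if any grade leads to treatment discontinuation. Pulmonary infections are not on its list.
- At Grade 2 the tables differ between holding and maintaining, and neither is a discontinuation.
- At Grade ≥3 pneumonitis, Table 2 discontinues umbralisib on any reading.
- Whether stopping one drug counts as treatment discontinuation is a wording question in Section 4.2. The two tables do not create it.

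**Conclusion.** The contradiction on ublituximab at Grade 2 is real, and the text is wrong as written. It rests on one assumption, that *all therapy* includes ublituximab, which the contrast with every other interruption row supports. For Grade ≥3 events the tables do not match on discretion or restart threshold. For Grade ≥3 pneumonitis it is unclear whether the discontinuation overrides Table 3's resumption and the rule that the other drug may continue. The Grade 1 pneumonitis sentence is a smaller defect of placement and completeness.

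The number of affected subjects cannot be estimated. A reader might take the 1% to 10% band that Section 7.2.1.2 gives for pneumonitis, pneumonia and bronchitis and apply it to 50 subjects: 0.01 × 50 = 0.5 to 0.10 × 50 = 5 per event type. That range does not measure this problem. The band is not split by grade, and it comes from 75 subjects followed for up to 3 years or more, so it includes Grade 1 events and events later than Cycle 12. Nor do the documents give any basis for an effect on ORR, and none is claimed.

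**What to change.** Reconcile Section 6.3, Table 2 and Table 3 so that each pulmonary grade carries one consistent instruction for each drug. Name the drug or drugs meant by *all therapy* and by the instruction to discontinue therapy. Make clear how that discontinuation relates to the rule that the other drug may continue. Resolve the Grade 1 pneumonitis sentence in the same pass, and confirm that the note belonging to the pulmonary asterisk is present and consistent with the rows. The sponsor's medical team chooses the clinical rule; this review proposes none. The cost is amendment wording and a memo to sites, with no new data and no additional subjects.

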6.3.2 DOSE DELAY/MODIFICATIONS: UBLITUXIMAB

No reduction in the dose of ublituximab is permitted. Please refer to Section 6.2.2.1 for detailed information on infusion rate guidance for infusion related reactions related to ublituximab.

Supportive care should be considered for any subject who experiences Grade ≥ 2 cytopenias, or Grade ≥ 1 non-hematologic toxicities. A delay for recovery from toxicity is allowed for both study drugs (individually or together) for recovery of hematologic toxicities to \leq Grade 3 or non-hematologic toxicities to \leq Grade 2 or to baseline level. If the subject withdraws consent or has documented progression, an end of study visit should be completed.

If Grade 4 anaphylaxis is observed at any point during ublituximab treatment, permanently discontinue ublituximab treatment and intervene as per investigator discretion.

If a subject discontinues only one study drug (either ublituximab or umbralisib), the subject may continue treatment with the other study drug per the protocol. **Contact the sponsor prior to discontinuing the study drug(s).**

TABLE 3: UBLITUXIMAB DOSE DELAY AND/OR MODIFICATIONS GUIDANCE

NCI-CTCAE Grade	Dose Delay and/or Modification
Hematologic Adverse Event	
Neutropenia	
Grade \leq 3 neutropenia	Maintain current dose. Consider supportive care as warranted.
Grade 4 neutropenia or occurrence of neutropenic fever or infection	Delay ublituximab until Grade \leq 3 and/or neutropenic fever or infection is resolved; consider growth-factor support as warranted; thereafter, resume at full dose.
Thrombocytopenia	
Grade \leq 3 thrombocytopenia	Maintain current dose and provide supportive care as clinically warranted.
Grade 4 thrombocytopenia	Delay ublituximab until Grade \leq 3; consider intervention with supportive care as warranted; thereafter resume at full dose.
Non-Hematological Adverse Events	
Grade \leq 2	Maintain current dose.
Grade \geq 3	Withhold ublituximab until Grade \leq 2 at the discretion of the investigator; consider supportive care intervention as warranted. Resume at full dose.

6.4 ORDERING UBLITUXIMAB AND UMBRALISIB

Once a clinical study site receives the open to enrollment letter and a subject is identified, a pre-determined quantity of ublituximab and umbralisib will be shipped to the site.

Upon receipt of this shipment, the Pharmacist or the appropriate person at the site should update the accountability forms for both ublituximab and umbralisib. If there is any abnormality in the supplied boxes (ublituximab) or bottles (umbralisib), the Pharmacist or the appropriate person must document it during the acknowledgement of receipt and contact the Sponsor and/or Sponsor designee.

6.5 DURATION OF THERAPY

Subjects will visit the study center as per the treatment schedule that is included in the protocol. All visits should occur as close as possible to the time specified in the protocol. Complete listings of the assessments that will be performed at each visit, during the trial treatment period, are specified in Section 5.

UTX-TGR-203

Dated: 20 December 2018 (Ver 2.0)

Page 43 of 85

In the absence of treatment delays due to adverse event(s), umbralisib and ublituximab should continue as per the treatment plan unless one of the following criteria applies:

- Disease progression or inter-current illness that prevents further treatment.
- Subject decides to withdraw from the study, or changes in the subject's condition render the subject unacceptable for further treatment in the judgment of the investigator.

7 STUDY MEDICATION OVERVIEW AND SAFETY

7.1 UMBRALISIB (TGR-1202)

Classification:	Phosphatidylinositol-3-Kinase (PI3K) Delta Inhibitor
Formulation:	See Investigator Brochure
Mode of Action:	Irreversibly inhibits activity of the Class I Delta isoform of PI3K
How Supplied:	Umbralisib: 200 mg tablets
Storage:	Store at 25°C. Excursions permitted 15°C to 30°C.
Stability:	Retest dates will be provided periodically by Sponsor.
Route of Administration:	Oral
Packaging:	Umbralisib is provided in HDPE bottles each containing 30 tablets and a silica gel canister as a desiccant.
Availability:	Umbralisib is available from TG Therapeutics.

7.2 UBLITUXIMAB

Chemical Name:	Ublituximab
Other Names:	TG-1101
Classification:	Recombinant chimeric anti-CD20 monoclonal antibody
Mode of Action:	Targets CD20 antigen on B-cells
Description:	Ublituximab is a genetically engineered chimeric murine/human mAb directed against the CD20 antigen found on the surface of B lymphocytes. Ublituximab displays the typical structure of immunoglobulins, consisting of two gamma (γ) heavy chains and two kappa (κ) light chains linked by disulfide bridges. It is composed of a murine variable region (37.2% of total amino acids) fused onto human constant regions.
How Supplied:	Concentration of 25mg/mL in 6 mL (150 mg) single-use glass vials.
Storage:	Ublituximab must be stored in a secured, limited-access, refrigerated area at a temperature ranging from +2°C / + 8°C. Ublituximab must not be frozen.

Stability: Once a vial of ublituximab has been opened and/or diluted it must be used immediately. After dilution, ublituximab is stable in static conditions for 24 hours at 25°C, and in dynamic conditions it is stable for 8 hours at 25°C.

Ublituximab has a shelf-life of 36 months if stored between +2°C / + 8°C, based on stability data.

Route of Administration: Intravenous

Packaging: Ublituximab is packed in kits. Each kit contains:

- Six vials containing 150 mg solution of ublituximab in each or
- One vial containing 150 mg solution of ublituximab (for replacement if needed)

The container closure system for the vials containing 6 mL is a type I glass vial closed by a siliconized chlorobutyl rubber stopper sealed with an aqua plastic and aluminum cap

Availability: Ublituximab is available from TG Therapeutics.

7.2.1 UBLITUXIMAB + UMBRALISIB (TGR-1202) COMBINATION - COMPREHENSIVE ADVERSE EVENTS AND POTENTIAL RISKS LISTS (CAEPRS)

The following adverse events were observed in subjects treated with the combination of ublituximab + umbralisib and were considered at least possibly related to one or both of the study medications. The preliminary safety data as of May 1, 2018 is provided for a total of 75 subjects exposed to ublituximab + umbralisib with a maximum follow up of 3+ years. See the latest ublituximab and umbralisib Investigator's Brochures for updated safety information a complete list of all adverse events reported regardless of causality..

7.2.1.1 VERY COMMON (≥ 10%):

Blood and Lymphatic System Disorders: anemia, neutropenia

Gastrointestinal Disorders: diarrhea, nausea, vomiting

General Disorders and Administration Site Conditions: fatigue

Injury, Poisoning and Procedural Complications: infusion related reaction

Metabolism and Nutrition Disorders: decreased appetite

7.2.1.2 COMMON (≥ 1% - < 10%):

Blood and Lymphatic System Disorders: thrombocytopenia

Cardiac Disorders: cardiac failure congestive

Ear and Labyrinth Disorders: ear congestion, ear discomfort

UTX-TGR-203

Dated: 20 December 2018 (Ver 2.0)

Page 46 of 85

Eye Disorders: conjunctival pallor, conjunctivitis, corneal oedema, vision blurred

Gastrointestinal Disorders: abdominal discomfort, abdominal distension, abdominal pain, constipation, dyspepsia, flatulence, gastrooesophageal reflux disease, haematochezia, salivary hypersecretion, stomatitis

General Disorders and Administration Site Conditions: asthenia, chills, face oedema, infusion site pain, local swelling, oedema peripheral, pyrexia, systemic inflammatory response syndrome

Hepatobiliary Disorders: hyperbilirubinaemia

Immune System Disorders: hypogammaglobulinaemia

Infections and Infestations: bronchitis, cellulitis, clostridium difficile colitis, enterocolitis infectious, oral candidiasis, oral herpes, otitis media, pneumonia, pneumonia streptococcal, rhinovirus infection, sepsis, sepsis syndrome, sinusitis, skin infection, upper respiratory tract infection, urinary tract infection

Injury, Poisoning and Procedural Complications: wound

Investigations: alanine aminotransferase increased, aspartate aminotransferase increased, blood alkaline phosphatase increased, blood creatinine increased, computerised tomogram thorax abnormal, immunoglobulins decreased, weight decreased

Metabolism and Nutrition Disorders: dehydration, failure to thrive, hyperglycaemia, hyperuricaemia, hypokalaemia, hypophosphataemia

Musculoskeletal and Connective Tissue Disorders: joint swelling, muscle spasms, muscular weakness, myalgia, pain in extremity

Nervous System Disorders: dizziness, dysgeusia, headache, lethargy, sinus headache, somnolence

Psychiatric Disorders: agitation, anxiety

Renal and Urinary Disorders: micturition urgency, renal failure, renal failure acute

Reproductive System and Breast Disorders: scrotal cyst, semen discolouration

Respiratory, Thoracic and Mediastinal Disorders: choking, cough, dysphonia, dyspnea, epistaxis, hypoxia, oropharyngeal pain, pneumonitis, productive cough, sinus congestion

Skin and Subcutaneous Tissue Disorders: alopecia, cold sweat, dermatitis acneiform, dermatitis bullous, dry skin, ecchymosis, pruritus, rash, maculo-papular, rosacea, urticaria

Vascular Disorders: hypertension

